8.3.8 Changes to Planned Analyses

Any changes to the planned statistical analyses made prior to performing the analyses will be documented in an amended Phase 2 Statistical Analysis Plan approved prior to performing the analyses. Changes from the planned statistical methods after performing the analyses will be documented in the clinical study report along with a reason for the deviation.

9 Health Economics Outcomes

A formal health economics analysis may be completed as part of this trial study, given meaningful clinical results are obtained. This will take into consideration complication rates, quality of life, and resource utilization. The EQ-5D-3L, a generic quality of life measure, will be used to assess health utilities. Costs associated with the health care utilization measures may be estimated at all sites. These inputs may be used in health economics analysis performed.

10 Data Management

Data management processes and requirements remain the same as Phase 1 of the ADVANTAGE AF study and can be referenced in **Section 10** of the Phase 1 clinical investigational plan.

11 Core Laboratories and Independent Assessment

11.1 *Arrhythmia Core Laboratory*

Specified arrhythmic events will be analyzed by an ACL to determine if the episodes are associated with Detectable AF, AFL or AT.

During the ADVANTAGE AF Study, more than one ACL may be utilized to optimize equipment availability, vendor capacity or other factors as determined by BSC. Each vendor utilized will be described in the final study report.

11.1.1 *Study ECGs*

To ensure objective assessment of rhythm monitoring data, the following 12-lead ECG tracings for Non Roll-in Treatment subjects will be reviewed by the ACL and/or CEC and included as study data:

- ECGs obtained during the following assessments: Day 90 and Day 360
- ECGs submitted during monitoring and adjudication of adverse events
- ECGs submitted during the evaluation of potential arrhythmias during the effectiveness evaluation period.

11.2 *LUX-Dx Recordings*

Atrial arrhythmia episodes (asymptomatic and symptomatic) captured by the LUX-Dx ICM will be analyzed by BeatLogic Core Lab Adjudicator Tool for atrial arrhythmia rhythm determination, including episodes captured by LUX-Dx during the pre-defined time periods for the Primary Effectiveness Endpoint. Specified arrhythmic events recorded by LUX-Dx ICM may additionally be analyzed by independent experts for rhythm determination. The ADVANTAGE AF Phase 2 Statistical Analysis Plan will define the formal process for adjudication of recurrence episodes collected by LUX-Dx for the study for endpoint analyses.

11.3 *Cardiac Imaging Core Laboratory*

A qualified CICL will be established to receive, review, and assess any cardiac MRIs and CTs obtained for the evaluation of potential PV stenosis.

Baseline cardiac MRIs and CTs will only be read by the CICL if subsequent events result in follow-up imaging for the assessment of potential PV stenosis.

Pulmonary Vein Dimensions

Treated veins to be assessed will have the baseline and post-ablation assessments of standardized diameters (See definition of PV Diameter in **Section 23.2**).

Cardiac Imaging Data Review and Transmission

The CICL will analyze PV dimensions, calculate changes in dimensions, make available the primary data for review and transmit the PV dimensional analyses of each imaging study to the Sponsor for inclusion in the study dataset.

12 Deviations

Deviation requirements remain the same as Phase 1 of the ADVANTAGE AF study and can be found in **Section 12** of the Phase 1 clinical investigational plan.

13 Device Accountability

13.1 *Investigationally Labeled Test Devices*

Table 13.1-1 below shows a list of FARAPULSE PFA System components for which device accountability is required by the investigational site.

Table 13.1-1 : Device Accountability for the FARAPULSE PFA System

Component	Subcomponents
FARAWAVE PFA Catheter	1. FARAWAVE Pulsed Field Ablation Catheters (31mm and 35mm) 2. FARASTAR Catheter Connection Cable
FARAPPOINT PFA Catheter	1. FARAPPOINT Pulsed Field Ablation Catheters
FARASTAR PFA Generator and Related Equipment	1. FARASTAR Pulsed Field Ablation Generator 2. FARASTAR Recording System Module 3. FARASTAR Mapping System Module
FARADRIVE Steerable Sheath	FARADRIVE Steerable Sheath

Accountability requirements for investigational, commercially-available devices, and non-medical devices/components remain the same as Phase 1 of the ADVANTAGE AF study and can be referenced in **Section 13** of the Phase 1.

14 Compliance

Compliance requirements remain the same as Phase 1 of the ADVANTAGE AF study and can be referenced in **Section 14** of the Phase 1 clinical investigational plan.

14.1 *Institutional Review Board/ Ethics Committee*

Consistent with the requirements outlined Section 14.3 of the Phase 1 protocol, the investigational site will obtain the written and dated approval/favorable opinion of the IRB/EC/REB for the clinical investigation before recruiting subjects and implementing all subsequent amendments, if required.

A copy of the written IRB/EC/REB and/or regulatory authority approval of the protocol (or permission to conduct the study) and ICF, must be received by the sponsor before recruitment of subjects into the study and shipment of investigational product/equipment. Prior approval must also be obtained for other materials related to subject recruitment or which will be provided to the subject.

Any amendment to the protocol which may impact the conduct of the study and patient safety, including changes of study objectives, study design, patient population, sample sizes, study procedures, will require review and approval by the IRB/EC/REB before the changes are implemented to the study. All changes to the ICF will be IRB/EC/REB approved; a determination

will be made regarding whether a new ICF needs to be obtained from subjects who provided consent, using a previously approved ICF.

Annual IRB/EC/REB approval and renewals will be obtained throughout the duration of the study as required by applicable local/country laws or regulations or IRB/EC/REB requirements. Copies of the study reports and the IRB/EC/REB continuance of approval must be provided to the sponsor. any amendment to the protocol which may impact the conduct of the study and patient safety, including changes of study objectives, study design, patient population, sample sizes, study procedures, will require review and approval by the IRB/EC/REB before the changes are implemented to the study. All changes to the ICF will be IRB/EC/REB approved; a determination will be made regarding whether a new ICF needs to be obtained from subjects who provided consent, using a previously approved ICF.

15 Monitoring

Monitoring requirements remain the same as Phase 1 of the ADVANTAGE AF study and can be referenced in **Section 15** of the Phase 1 clinical investigational plan.

16 Potential Risks and Benefits

16.1 Anticipated Adverse Events

Based upon the current literature, prior reports on adverse events with an ablation catheter, and available data on clinical use of the FARAPULSE PFA System, below is an alphabetical list of the possible anticipated adverse events and possible adverse device effects associated with ablation with the FARAPULSE PFA System for the treatment of PersAF and adjunctive ablation of the CTI for isthmus-mediated AFL. The occurrence of any of the listed events could lead to harm, the need for intervention, or prolonged hospitalization for the subject.

These anticipated events may be caused by or associated with the proposed use of the investigational devices and other devices, the failure, misuse or malfunction of the investigational devices or other devices, or the related procedures stipulated by this protocol or associated with this clinical study. There may also be additional risks which are unknown at this time.

- Access site complications (e.g., hematoma, fistula, pseudo-aneurysm, laceration, bleeding) potentially requiring surgical intervention
- Allergic reaction or fever resulting from contact with catheters or drugs
- Anemia
- Arrhythmia, potentially requiring cardioversion, defibrillation, or rhythm management device
- Arteriovenous fistulah
- Back pain
- Bed sores
- Bleeding, hematoma, hemorrhage, or aneurysm at vascular access sites
- Blood pressure changes including hypotension or hypertension
- Cardiac tamponade or perforation
- Cardiac arrest or cardiac failure
- Cardiogenic shock

- Catheter entrapment/impingement potentially requiring endovascular or surgical intervention
- Conduction system injury, either transient or permanent, potentially requiring pacemaker insertion
- Coronary artery or vein injury
- Damage to cardiac structure
- Death
- Esophageal injury, ulcer, or fistula
- Gastric motility / pyloric spasm disorders
- Harmful large muscular contraction
- Heart failure
- Hemodynamic compromise
- Hemopericardium
- Hemoperitoneum
- Hemothorax
- Local infection, systemic infection and / or sepsis
- Muscle contractions due to electric stimulation
- Myocardial infarction / ischemia
- Nerve damage
- Organ failure
- Pain
- Perforation (e.g., of diaphragm, liver, and lung).
- Pericardial effusion
- Pericarditis
- Peritonitis
- Phrenic nerve injury with potential paralysis of the diaphragm and breathing impairment
- Pneumomediastinum
- Pneumopericardium
- Pneumoperitoneum
- Pneumothorax
- Procedural delay
- PV injury, perforation, or stenosis
- Respiratory Distress
- Risk of cancer or birth defect / harm to fetus from x-ray exposure
- Skin burns / irritation from X-ray exposure
- Stroke / TIA
- Surgical procedure to correct any anticipated AE
- Thrombosis
- Vessel damage, dissection, or occlusion.
- Vessel obstruction due to thrombus, debris, introduction of gas, or vascular spasm

16.2 Anticipated Adverse Events – LUX-Dx ICM

As part of study participation, subjects must have a commercially available LUX-Dx inserted for arrhythmia monitoring. Potential adverse events related to the insertion of the device are provided in the User's Manual. These risks for subjects participating in the ADVANTAGE AF study do not differ from those subjects with a LUX-Dx ICM insertion not participating in the trial.

16.3 Risks Associated with the Study Device(s)

Benchtop studies, pre-clinical research, feasibility studies, and CE Mark clinical studies have demonstrated that the FARAPULSE PFA System is safe for human use. Potential risks have been evaluated and mitigation strategies have been implemented to reduce potential risks to acceptable levels.

16.4 Risks associated with Participation in the Clinical Study

The investigational aspects related to the use of the FARAPPOINT Catheter in the ADVANTAGE AF Phase 2 study may increase the risk of coronary artery spasm. There may also be additional risks which are unknown at this time.

16.5 Possible Interactions with Concomitant Medical Treatments

Anti-arrhythmic and anticoagulant medications included in ADVANTAGE AF procedures are all approved for their indicated uses in the relevant geography. Therefore, there is no foreseen increased risk to subjects for participating in the ADVANTAGE AF Study.

16.6 Risk Minimization Actions

Additional risks may exist. Risks can be minimized through compliance with this protocol, performing procedures in the appropriate hospital environment, ensuring that an interventional cardiologist and cardiac catheterization laboratory are available, adherence to subject selection criteria, close monitoring of the subject's physiologic status during research procedures and / or follow-ups and by promptly supplying BSC with all pertinent information required by this protocol. The use of nitroglycerin as described in Section 7.7.2.5 is intended to minimize the risk of harm from vascular spasm related to the investigational use of the FARAPPOINT Catheter. Additionally, sites should ensure availability of co-oximetry to perform the diagnosis of methemoglobinemia and methylene blue to potentially treat the condition for subjects undergoing the nitroglycerin workflow when treated with the FARAPULSE PFA Catheter.

16.7 Anticipated Benefits

Subjects may or may not receive any benefit from participating in the ADVANTAGE AF Study as compared to the current standard of care received for treatment of PersAF. Potential benefits of the FARAPULSE PFA System for the subject may include the following:

- Complete or partial reduction in symptoms related to PersAF
- Complete or partial reduction in the number of cardioversions, medications a subject is taking, and in the number of hospitalizations related to PersAF
- Treatment using an investigational device which has demonstrated the ability to isolate PVs and the PW endocardially, to reduce the subsequent occurrence of symptomatic AF in treated

subjects and potentially to reduce the risk for severe ablation complications associated with thermal ablation such as phrenic nerve palsy or atrio-esophageal fistula.

16.8 Risk to Benefit Rationale

Risk management activities, including Hazard Analyses (HA) and Failure Mode Effects Analyses (FMEA), have been performed on the FARAPULSE PFA System and its components to identify and analyze known and foreseeable hazards (in both normal and fault conditions) and reasonably foreseeable sequences or combinations of events that could result from using this product and the risks associated with each hazard. Mitigations have been implemented in the design, processes, and / or labeling and directions for use of the product to reduce the residual risk of each hazard as necessary and practicable. The HA has been reviewed and approved and the remaining risks are acceptable when weighed against the anticipated benefits to the subject.

17 Safety Reporting

Safety, device deficiency, and death reporting requirements and definitions remain the same as Phase 1 of the ADVANTAGE AF study and can be referenced in **Section 17** of the Phase 1 clinical investigational plan.

17.1 Reportable Events by Investigator to BSC

In addition to those events defined in Section 17.1 of the Phase 1 ADVANTAGE AF study, it is the responsibility of the Investigator to assess and report to BSC any event which occurs in any of following categories:

- The occurrence of ST elevation or clinical signs of ischemia or injury for those subjects receiving treatment for CTI-mediated AFL with the FARAPPOINT Catheter as a component of the FARAPULSE PFA System.
- All study procedure related events, related to the LUX-Dx ICM insertion procedure.

The start of the FARAPULSE™ Index study procedure is defined as the point in which the investigational device is inserted into the subject's body.

17.2 Investigator Reporting Requirements

In addition to those events defined in Section 17.4 and Table 17.4-1 of Phase 1 of the ADVANTAGE AF study, the following must be reported as described in Table 17.2-1 of Phase 2 of the ADVANTAGE AF study.

Table 17.2-1: Investigator Reporting Requirements

Event Classification	Communication Method	Communication Timeline Pre-Market Studies*

For those subjects receiving treatment for CTI-mediated AFL with the FARAPPOINT Catheter as a component of the FARAPULSE PFA System:
 
 Angiography performed with visualization of severe ($\geq 70\%$) spasm ST elevation, defined by ST elevation of 2mm in two contiguous leads and adjudicated to be a result of coronary spasm Cardiac arrest adjudicated to be a result of coronary spasm. 	
Complete AE eCRF page with all available new and updated information.
 
Provide all relevant source documentation (de-identified/ pseudonymized) for reported event.
	
 Immediately, but not later than 3 calendar days of first becoming aware of the event or as per local/regional regulations. Reporting required through the end of the study 
 When documentation is available. Upon request of Sponsor.

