VT/VF occurring during ablation with the FARAPULSE PFA System	Complete AE eCRF page with all available new and updated information, including the location and number of all PFA energy deliveries.	
 • Immediately, but not later than 3 calendar days of first becoming aware of the event or as per local/regional regulations. • Reporting required through the end of the study
	Provide all relevant source documentation (de-identified/ pseudonymized) for reported event.	
 • When documentation is available • Upon request of Sponsor
Device Deficiencies (including but not limited to malfunctions, use errors and inadequacy in information supplied by the manufacturer, including labeling) Note: Any Device Deficiency that might have led to a serious adverse event if appropriate action had not been taken, intervention had not occurred, circumstances had been less fortunate is considered a reportable event.	Complete Device Deficiencies eCRF with all available new and updated information.	
 • Immediately, but not later than 3 calendar days of first becoming aware of the event. • Reporting required through the end of the study
	Provide all relevant source documentation (de-identified/ pseudonymized) for reported event.	
 • Upon request of Sponsor

Event Classification	Communication Method	Communication Timeline Pre-Market Studies*
Adverse Event including Adverse Device Effects	Complete AE eCRF page, which contains such information as date of AE, treatment of AE resolution, assessment of seriousness and relationship to the device.	
 Adverse Device Effects (or other key events of interest): In a timely manner but not later than 10 business days after becoming aware of the information Adverse Events: In a timely manner but recommend within 10 business days after becoming aware of the information Reporting required through end of study Upon Sponsor request
	Provide all relevant source documentation (de-identified/pseudonymized) for reported event, as requested by Sponsor.	

* Note that pre-market studies are clinical studies with investigational devices or with medical devices that bear regulatory approval but are not being used for an approved indication. (21 CFR Part 812, MDCG 2020-10/1)

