19.2 Clinical Events Committee

A Clinical Events Committee (CEC) is an independent group of individuals with pertinent expertise that will adjudicate events reported by study Investigators and their relationship toward potential primary endpoints.

- All deaths
- All Serious Adverse Events
- All adverse events included in the composite primary safety endpoint per **Section 3.2** of this protocol
- All adverse events that are potentially related to the procedure or any of the devices included in the FARAPULSE PFA System
- All unanticipated device effects.
- Other events at the discretion of BSC

Committee members will include practitioners of Electrophysiology (EP), and / or Cardiology, as well as other experts with the necessary therapeutic and subject matter expertise to adjudicate the event categories outlined above. A complete description of CEC responsibilities, qualifications, membership, and committee procedures will be outlined in the CEC charter.

The CEC will review a safety event dossier, prepared by BSC, which may include copies of subject source documents provided by study sites, core lab results and independent reviewer information as available for the above listed events. For purposes of determining inclusion into the primary safety endpoint, the CEC will adjudicate all the above listed events as to their level of seriousness and relation to the ablation procedure and / or catheter. All supporting source documentation provided by the center will be sent to the CEC for adjudication as defined in the CEC charter. The CEC's adjudication of study adverse event data is final.

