7.7.2.5 CTI Ablation

The following subjects will undergo CTI ablation with the FARAPoint PFA Catheter:

- Required: For subjects with a history of CTI-mediated (typical) AFL and
 - Who have not had a CTI ablation procedure, or
 - Who have had a CTI ablation procedure but have recurrent CTI conduction.
- Required: Subjects who manifest CTI-mediated AFL (spontaneous or induced) during the Index Procedure
- At Investigator discretion: Subject welfare indicates that CTI ablation should be performed.

CTI Ablation with the FARAPoint PFA Catheter will be performed according to the IFU documents and institutional practice. Per the FARAPoint Catheter IFU, no more than two energy applications should be delivered at any given catheter placement. Repeat placement of the FARAPoint Catheter at nearly identical locations should be avoided unless there is a clear clinical need for such placements.

The FARAWAVE Catheter is not allowed to complete any CTI lesion.

CTI ablation with the FARAPoint PFA Catheter must adhere to the following protocol requirements in order to mitigate the risk of coronary spasm during ablation application.

No ablations outside CTI with the FARAPoint PFA Catheter are allowed.

The following prophylactic workflow is required to be followed when CTI ablation is performed with the FARAPoint PFA Catheter:

- **Pre-Treatment (Required)**: Administer a three milligrams (3mg) nitroglycerin IV bolus via the FARADRIVE sheath (or other sheath with central access) approximately one minute prior to the first PFA application at the anterior position of the CTI line.
- **During Ablation (Required)**:

⁷ If anesthesia necessitates, a pre-discharge fluoroscopic sniff test or inspiration / expiration CXR may be acceptable. See **Section 7.8**.

- Depending upon procedure duration and patient condition, administer an additional 2mg IV bolus via the FARADRIVE sheath (or other sheath with central access) approximately two (2) minutes apart until the ablation is complete or a maximum total of 9mg IV of nitroglycerin has been administered.
- If bidirectional block (BDB) is assessed and not present and additional ablation lesions are required in the anterior aspect of the cavo-tricuspid isthmus line, Investigator discretion will determine whether to administer an additional 2-3 mg of nitroglycerin IV via the FARADRIVE sheath (or other sheath with central access) prior to re-ablation.

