17.3 Reporting to Regulatory Authorities / IRBs / ECs / REBs / Investigators

In addition to those events defined in Section 17.6 of Phase 1 of the ADVANTAGE AF study, BSC is responsible for reporting adverse event information to all participating Principal Investigators, IRBs / ECs / REBs and regulatory authorities, as applicable. Sponsor reporting to the FDA will adhere to applicable requirements, including 10 working days following Sponsor awareness for occurrence of ST elevation or clinical signs of ischemia or injury for those subjects receiving treatment for CTI-mediated AFL with the FARAPPOINT Catheter as a component of the FARAPULSE PFA System.

18 Informed Consent

Informed consent requirements remain the same as Phase 1 of the ADVANTAGE AF study and can be referenced **Section 18** of the Phase 1 clinical investigational plan.

19 Committees

The safety monitoring operations team, clinical events committee, data monitoring committee and executive steering committee will operate in the same manner for Phase 2 of the ADVANTAGE AF study as defined in Phase 1. Refer to **Section 19** of the Phase 1 clinical investigational plan for additional information.

20 Suspension or Termination

Suspension and termination requirements remain the same as Phase 1 of the ADVANTAGE AF study and can be referenced in **Section 20** of the Phase 1 clinical investigational plan.

21 Study Registration and Results

Study registration and results requirements remain the same as Phase 1 of the ADVANTAGE AF study and can be referenced in **Section 21** of the Phase 1 clinical investigational plan.

22 Reimbursement and Compensation for Subjects

Reimbursement and subject compensation requirements remain the same as Phase 1 of the ADVANTAGE AF study and can be referenced in **Section 22** of the Phase 1 clinical investigational plan.

23 Abbreviations and Definitions

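### In Appendix A Table 17.2-1, 3-day reporting of ST elevation after FARAPOINT depends on an adjudication that normally follows the report, so non-serious events fall to the 10-business-day row

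*Combined protocol and SAP*

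**What the plan says.** Appendix A handles ischemia after FARAPOINT in three consecutive sections.

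- **Section 17.1** lists what the investigator must report: "The occurrence of ST elevation or clinical signs of ischemia or injury". It sets no millimetre threshold, no adjudication condition and no deadline.
- **Section 17.2, Table 17.2-1** sets a deadline of 3 calendar days from first awareness for three events. The first begins "Angiography performed with visualization of severe" spasm and carries no adjudication condition. The second is "ST elevation, defined by ST elevation of 2mm in two contiguous leads and adjudicated to be a result of coronary spasm". The third is "Cardiac arrest adjudicated to be a result of coronary spasm".
- **Section 17.3** commits the sponsor to inform FDA within "10 working days following Sponsor awareness for occurrence of ST elevation or clinical signs of ischemia or injury", again without adjudication.

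Appendix A states that Table 17.2-1 adds to main protocol Table 17.4-1 and does not replace it. Table 17.4-1 requires serious adverse events and serious adverse device effects within 3 calendar days, and unanticipated device effects within 1 business day. For non-serious adverse device effects it says "In a timely manner but not later than 10 business days after becoming aware of the information". For other non-serious adverse events, 10 business days is only recommended.

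Main protocol Section 19.2, carried into Phase 2 by Appendix A Section 19, says that the Clinical Events Committee "will adjudicate events reported by study Investigators".

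**The concern.** The ST-elevation entry in Table 17.2-1 is worded identically to one limb of the Coronary Spasm Events endpoint in Appendix A Section 3.5.1. A definition meant for classifying events after review is serving as the trigger for a report that comes before review. On the day a site sees ST elevation, nobody has normally adjudicated it, so the 3-day row does not apply on its terms.

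Coronary artery spasm is the one specific added risk of participation that Appendix A Section 16.4 names. Section 7.7.2.5 also requires a 12-lead ECG after CTI ablation to look for ischemia. The plan therefore looks for this signal but gives its non-serious form no workable expedited route to the sponsor, and the FDA clock starts only when the sponsor knows.

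**Working it through.** The plan gives no figure to reproduce. The check traces the reporting routes and then converts the stated limits to calendar days.

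**Step 1: which deadline applies when the site first becomes aware.**

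| Event after FARAPOINT | Route | Deadline |
|---|---|---|
| Cardiac arrest, any cause | Life-threatening, hence a serious adverse event (main protocol Tables 17.2-1 and 17.4-1) | 3 calendar days |
| ST elevation or ischemia meeting any seriousness criterion | Same | 3 calendar days |
| Severe spasm seen on angiography | Appendix A Table 17.2-1 | 3 calendar days |
| Non-serious ST elevation or signs of ischemia, not adjudicated, no severe spasm on angiography, judged device-related | Main protocol Table 17.4-1, adverse device effect | At most 10 business days |
| The same, judged not device-related | Main protocol Table 17.4-1, adverse event | 10 business days recommended |

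Only the last two rows are affected. Two other routes do not ordinarily catch them. The ECG criterion for myocardial infarction in Appendix A Table 3.3-2 needs changes lasting more than 1 hour, so briefer ST elevation does not meet it. Ischemia and vascular spasm are listed as anticipated in Appendix A Section 16.1, so the 1-business-day route for unanticipated effects would not normally apply. ST elevation under 2 mm and signs of ischemia without ST elevation have no entry in Table 17.2-1, with or without adjudication.

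**Step 2: size of the delay.** Assumptions: business days are Monday to Friday, there are no public holidays, each party uses its full limit, and the sponsor becomes aware on the day the site reports.

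- Site to sponsor: 10 business days from a weekday is two working weeks, or 14 calendar days. Delay = that figure minus 3.
- Site to FDA: add the sponsor's 10 working days to each route.

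| Day of awareness | 10 business days, in calendar days | Delay against 3 days | To FDA via 10 business days | To FDA via 3 days |
|---|---|---|---|---|
| Mon, Tue, Fri | 14 | 11 | 28 | 17 |
| Wed | 14 | 11 | 28 | 16 |
| Thu | 14 | 11 | 28 | 15 |
| Sat | 13 | 10 | 27 | 17 |
| Sun | 12 | 9 | 26 | 17 |

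The latest report to the sponsor is thus 9 to 11 calendar days later. The latest report to FDA comes at 26 to 28 days after site awareness instead of 15 to 17.

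**Step 3: comparison inside the plan.** For ventricular tachycardia or fibrillation during ablation, main protocol Section 17.1, Table 17.4-1 and Section 17.6 all name the same event, none with an adjudication condition. For ischemia after FARAPOINT, Appendix A 17.1 and 17.3 match each other and Table 17.2-1 does not.

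**The case against.** The strongest reply is that Table 17.2-1 is an addition. A reader might infer that cardiac arrest must wait for adjudication, or that this table is the only source of a 3-day clock. Neither is so. Cardiac arrest is serious whatever its cause, and Table 17.4-1 already makes it due in 3 calendar days; the same holds for any serious ischemic event. This stands in full and confines the point to non-serious events.

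Second, the table does not say who adjudicates, and Section 17.1 asks the investigator to assess as well as report. If the investigator's own judgement counted, some events could meet the row on the day. This stands as a limit on certainty. It does not remove the problem, because the only adjudicating body described in Section 19.2 acts after the report, and events of unclear cause would still fall outside.

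Third, the 10-business-day row sets a ceiling and asks for timely reporting, and detection at the site is not delayed: ischemic ECG changes after CTI ablation require a same-day echocardiogram. Both are correct. The figures above are maximum lags.

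Two stronger readings of the impact are also tempting.

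- One could compute (80 + 0.30 × 258) / 26 weeks = about 6 FARAPOINT subjects per week, and so about 8 to 10 treated in 9 to 11 days. That assumes even accrual and describes enrollment during a maximum lag. Nothing in the documents pauses treatment after a single non-serious ST elevation, so these are not subjects the fix would spare.
- One could take the 20 subjects in Appendix A Section 1.2 as all prior FARAPOINT experience. The same section describes a further European study that includes CTI interruption, without giving its size or catheter, so the total is not established.

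Finally, 17.1, Table 17.2-1 and 17.3 all refer to treatment for CTI-mediated flutter, while Section 7.7.2.5 also allows ablation thus: "At Investigator discretion: Subject welfare indicates that CTI ablation should be performed". A reader might conclude that discretionary cases are excluded. Section 4.1.2 suggests that the phrase is a general label: it expects about 30% of Treatment Subjects (0.30 × 258 = 77) to receive FARAPOINT for CTI-mediated flutter, close to its estimate of 80 treated with the catheter. This needs clarifying but is not a demonstrated gap.

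**Conclusion.** The point holds for non-serious ST elevation and non-serious signs of ischemia. For these, the trigger in Table 17.2-1 normally cannot be satisfied when the clock should start, and the table disagrees with the sections on either side of it. The consequence is a latest report to the sponsor at 12 to 14 calendar days instead of 3 for adverse device effects, and no firm deadline for events judged unrelated.

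This rests on reading the adjudicator as the Clinical Events Committee, which is an inference from Section 19.2, and on the calendar assumptions stated above. The row that catches these events also covers further key events of interest that are not defined, so sites may vary in how they use it. The primary hypotheses, sample size and error rate are not affected. The correction is worth making because it lets a safety-reporting rule work for the one added risk that Appendix A singles out.

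**What to change.** 1. In Appendix A Table 17.2-1, delete the adjudication condition from the ST-elevation entry. Keep adjudication only in the Section 3.5.1 endpoint definition, and name the adjudicator there.
2. Reconcile the event definition in Table 17.2-1 with Sections 17.1 and 17.3. In particular, state which deadline applies to ST elevation under 2 mm and to clinical signs of ischemia without ST elevation.
3. As a clarification, state in 17.1, Table 17.2-1 and 17.3 that they cover every subject given FARAPOINT CTI ablation, including at investigator discretion.

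Removing the adjudication words from the cardiac arrest entry would tidy the table but change no deadline.

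The cost is a wording amendment and a prompt on the adverse event form. The downside is a few more expedited reports that are later adjudicated as not due to spasm.
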